The Avaluus™ (Medtronic, Minneapolis, MN) is one of most recently introduced stented bovine pericardial bioprostheses. [2] A prospective observational study, which is called PERIGON (PERIcardial SurGical AOrtic Valve ReplacemeNt) Pivotal Trial, have reported favorable 5-year hemodynamic performance and clinical outcomes after AVR using the Avaluus™ valve.⁴ However, there has been no study that prospectively compared results after AVR using the Avaluus™ with those after AVR using other bovine pericardial valves.

To perform a comparative analysis for the efficacy and safety of this newly introduced bioprosthetic, a prospective randomized controlled trial (RCT) comparing the Avaluus™ with the world-wide used Carpentier-Edwards PERIMOUNT Magna Ease (CEPME; Edwards Lifesciences, Irvine, CA) was designed by the authors.

2) Hypothesis and Objectives

The present study is conducted to compare 1-year hemodynamic performances after AVR using the AvaluTM valve with those using the CEPME.

We hypothesize that the AvaluTM was noninferior to the CEPME based on the mean pressure gradient across the aortic valve (AVMPG) at 1-year echocardiographic follow-up.

9. Inclusion criteria, Exclusion criteria and Sample size calculation

1) Inclusion criteria

- ① Patients who are scheduled to undergo AVR
- ② Over 19 years of age
- ③ Patients who are planned to receive a bioprosthetic valve for aortic valve substitute
- ④ Patients who or whose legal representative fill out a written consent form before the start of the clinical trial and patients who can comply with the clinical trial requirements

2) Exclusion criteria

- ① Patients with concomitant mitral or tricuspid valve operation
- ② Patients with severe left ventricular dysfunction (ejection fraction < 0.30)
- ③ Patients with infective endocarditis
- ④ Patients with a medical history such as a malignant disease that might limit the possibility of mid-term follow-up
- ⑤ Patients who refused study enrollment

3) Sample size calculation

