Surgeries are performed under median sternotomy or upper partial sternotomy under cardiopulmonary bypass with cold cardioplegic arrest. After the diseased AV is excised, the annulus is prepared for landing the prosthesis, and the proper valve sizes for both types of

prostheses are decided before randomization. Then, randomization is performed with a web-based block randomization method with randomly determined block sizes of 4 and 6. After randomization, the assigned prosthesis is implanted with non-everting transverse mattress sutures. The knot-tying is performed manually or by using an automated knot-fastener.

Patients are evaluated with early clinical outcomes and early echocardiographic measurements. After discharge, all patients undergo regular postoperative follow-up through the outpatient clinic at 3- to 6-month intervals and are interviewed by telephone for confirmation of their condition if the last clinic visit has not been conducted as scheduled. At postoperative 1-year, clinical outcomes and echocardiographic measurements are evaluated as scheduled.

※ Randomization : Patients who meet the inclusion criteria and the exclusion criteria are randomly assigned to 1 of the 2 bioprostheses in a 1:1 manner. Randomization is performed with a web-based block randomization method (<https://mrcc.snuh.org/>) with randomly determined block sizes of 4 and 6, considering the institution as a stratification factor.

2) Outcome measures

- 1) Demographics: age, sex, height, weight, BMI, BSA, diagnosis, operation name
- 2) Preoperative data
 - Risk factors: DM, HTN, smoking, dyslipidemia, stroke, COPD, CKD, chronic liver disease, coronary disease, peripheral vascular disease, history of cardiac surgery, New York Heart Association functional class, STS mortality risk, EuroSCORE II
 - Echocardiographic measurements: Effective orifice area, mean pressure gradient, peak pressure gradient, LA dimension, LV ejection fraction, LV end diastolic dimension, LV end systolic dimension, pulmonary artery systolic pressure, TR severity, etc.
 - Electrocardiography
 - Laboratory tests: CBC, routine chemistry, NT-proBNP, CRP, ABGA, lactate, PT, aPTT
 - CT scan (thoracoabdominal CT angio)
 - Pulmonary function test
- 3) Operative data: CPB time, ACC time, concomitant procedures, operative findings
- 4) Postoperative data

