*** Predicted risks**

Because both prostheses have proved their efficacy and safety by prospective pivotal trials

and many related studies, the predicted risks associated with the present study will be comparable to routinely performed aortic valve replacement.

If any adverse event or risk occurs, providing the standard management for them will be sufficient.

5) Criteria for suspension and dropout

Patients who decline to participate in the trial are suspended or drop-out

6) Safety

Safety outcomes will be a composite of death from any cause and individual major postoperative complications including low cardiac output, bleeding reoperation, perioperative myocardial infarction, perioperative stroke, acute kidney injury, respiratory complications, postoperative atrial fibrillation, and mediastinitis.

All safety outcome measures will be assessed and recorded at designated time intervals by research personnel at each individual center. Data regarding every event will be reviewed and adjudicated centrally by the principal investigator and sub-investigator.

7) Efficacy

Efficacy analysis will be performed for ITT(Intention to treat) group, and supplemental analysis will be performed for PP(Per protocol) and As treated group. The primary endpoint will be concluded as 'noninferior' if both ITT and PP analyses confirm the noninferiority.

ITT group includes all study population. PP group is constituted from the ITT group after excluding the patients with major violation of the study protocol.

The null hypothesis was that the Avalus™ was inferior to the CEPME based on the AVMPG at 1-year echocardiographic follow-up, with a non-inferiority margin of 3mmHg. The result for the primary endpoint was presented with 97.5% one-sided confidence interval for mean difference between groups. The non-inferiority test was performed using a t-test which compared mean difference between groups with the non-inferiority margin under the one-sided significance level of 0.025.

For analysis of 1-year clinical outcomes including all-cause mortality, cardiac death, and MAEs, events were counted at postoperative 1 year, and comparisons between the 2 groups were made using the chi-square test and Fisher's exact test. A P value of $< .050$ was considered statistically significant.

8) Schedules

- ① Study planning : October 1, 2018 – November 31, 2018
- ② Enrollment : January 1, 2019 (or after IRB approval) – June 30, 2022

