**Prospective Randomized comparison Of prosthetic Valve Effective
orifice area: One-year analysis of two bovine PERIcardial valves
(PROVE-PERI trial)**

NCT 03796442

Trial Protocol v 1.4

Updated Dec 28, 2018

Statistical Analysis Plan

1. Inclusion criteria

- ① Patients who are scheduled to undergo AVR
- ② Over 19 years of age
- ③ Patients who are planned to receive a bioprosthetic valve for aortic valve substitute
- ④ Patients who or whose legal representative fill out a written consent form before the start of the clinical trial and patients who can comply with the clinical trial requirements

2. Exclusion criteria

- ① Patients with concomitant mitral or tricuspid valve operation
- ② Patients with severe left ventricular dysfunction (ejection fraction < 0.30)
- ③ Patients with infective endocarditis
- ④ Patients with a medical history such as a malignant disease that might limit the possibility of mid-term follow-up
- ⑤ Patients who refused study enrollment

3. Sample size calculation

The study is designed to have 80% power to detect 1-year AVMPG of $12.6 \pm 4.3 \text{ mmHg}$ for the study prosthesis [1] and $11.9 \pm 4.3 \text{ mmHg}$ for the control prosthesis, [2] with a 1-sided type I error of 2.5% and a noninferiority margin of 3mmHg. The noninferiority margin was determined by the values of 15mmHg for AVMPG of clinically significant aortic stenosis [3] and 12mmHg for AVMPG of the control prosthesis. Fifty-six patients in each group were needed to complete the study cohort. Allowing for a 20% dropout rate during the 1-year follow-up, we determined that the recruitment of 70 patients in each group was necessary.

- (1) Level of significance (α) = 0.025
- (2) Type II error (β) = 0.20, power of the test = 80%
- (3) Drop out rate = 20%
- (4) One-tailed test

H_0 (null hypothesis): $\mu_1 - \mu_2 \geq \delta$

H_1 (alternative hypothesis): $\mu_1 - \mu_2 < \delta$

(μ_1 : mean AVMPG of the study group on 1 – year echocardiographic follow – up ,
 μ_2 : mean AVMPG of the control group on 1 – year echocardiographic follow – up
 δ : noninferiority margin)

The calculation was performed using PASS Software(Power Analysis and sample size software: <http://www.ncss.com>), and the calculated formula is as follows.

$$n = \frac{(Z_\alpha + Z_\beta)^2 (\sigma_1^2 + \sigma_2^2)}{(\mu_1 - \mu_2) - \delta}^2$$

μ_1 = mean AVMPG of the study group on 1 – year echocardiographic follow – up

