Statistical analyses will be performed using SPSS software (version 25.0; IBM, Armonk, NY) and SAS software (version 9.3; SAS Institute, Cary, NC). Data will be expressed as the mean \pm standard deviation, median with IQRs or proportions. Comparisons between the 2 groups will be made using the chi-square test and Fisher's exact test for categorical variables and Student's t-test or the Mann-Whitney test for continuous variables, as appropriate. The null hypothesis is that the AvaluTM is inferior to the CEPME based on the AVMPG at 1-year echocardiographic follow-up, with a non-inferiority margin of 3mmHg. The result for the primary endpoint is presented with 97.5% one-sided confidence interval for mean difference between groups. The non-inferiority test will be performed using a t-test which compares mean difference between groups with the non-inferiority margin under the one-sided significance level of 0.025. For analysis of 1-year clinical outcomes including all-cause mortality, cardiac death, and MAEs, events will be counted at postoperative 1 year, and comparisons between the 2 groups will be made using the chi-square test and Fisher's exact test. A P value of $< .050$ will be considered statistically significant. All outcomes will be compared with an intention-to-treat base. Per-protocol and as-treated analyses will be added for hemodynamic outcomes.

References

3. D Rennie. How to report randomized controlled trials. The CONSORT statement. *JAMA.* 1996;276:649.
4. Fiegl K, Deutsch MA, Rondak IC, Lange R, Guenzinger R. Matched Comparison of Two Different Biological Prostheses for Complete Supra-annular Aortic Valve Replacement. *Thorac Cardiovasc Surg.*

2015;63:459-66.

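### The primary noninferiority test is an unadjusted t-test although preoperative LVEF, BSA and sex are already collected; prespecified adjustment may gain precision at a small, bounded cost

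*SAP*

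**What the plan says.** The SAP's statistical analysis paragraph, which follows its sample size section, sets the primary test: "The non-inferiority test will be performed using a t-test which compares mean difference between groups with the non-inferiority margin". Protocol section 10, 7) Efficacy has the matching sentence: "The non-inferiority test was performed using a t-test which compared mean difference between groups with the non-inferiority margin". Both use a one-sided 0.025 level and a one-sided 97.5% confidence interval for the mean difference. Neither names a covariate, for the primary analysis or for any sensitivity analysis. The Efficacy section also requires both the ITT and the PP analysis to show noninferiority.

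The baseline data are listed in Protocol section 10, 2) Outcome measures. Item 1 reads "Demographics: age, sex, height, weight, BMI, BSA, diagnosis, operation name". Item 2, preoperative data, includes "Echocardiographic measurements: Effective orifice area, mean pressure gradient, peak pressure gradient, LA dimension, LV ejection fraction". LVEF has to be known at eligibility, because an ejection fraction below 0.30 is an exclusion (Protocol section 9, 2). Randomisation is stratified by institution only.

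**The concern.** A gradient across a valve depends on the flow through it as well as on the prosthesis. Flow depends in part on the ventricle and on body size. That is a physical reason, though not one given in the documents, to expect LVEF, BSA and sex to explain some of the between-patient variation in 1-year AVMPG. An unadjusted t-test leaves any such variation in its error term.

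The plan has little slack. It is sized at 80% power for 56 evaluable patients per arm after exactly 20% loss, and the test must succeed in two analysis sets. Nothing in the design balances LVEF or body size between arms, and nothing in the analysis allows for chance imbalance in them. If an imbalance does appear and no adjusted model was fixed in advance, any later adjustment is open to the charge that the covariates were chosen after seeing the results.

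**Working it through.** **Inputs from the documents** (SAP and Protocol sample size sections): SD 4.3 mmHg in both arms; assumed means 12.6 and 11.9, so a true difference of 0.7; margin 3, so a distance to the margin of 3 − 0.7 = 2.3 mmHg; "Level of significance (α) = 0.025", one-sided; 56 evaluable per arm; 20% dropout.

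**Assumed input:** R², the share of AVMPG variance explained by the covariates. The documents give no figure, so a range is shown.

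**1. Reproduce the plan's figure.**
- The plan's formula gives n = (1.960 + 0.842)² × 2 × 4.3² / 2.3² = 54.9, so 55 per arm.
- The noncentral t calculation gives 56 per arm, with power 80.1% (79.4% at 55).
- 56 / 0.80 = 70 recruited per arm.
- Standard error = 4.3 × √(2/56) = 0.813. Half-width = t(0.975; 110 df) × 0.813 = 1.982 × 0.813 = 1.61 mmHg.

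The stated sample size is correct for the stated test.

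**2. Formulas for the adjusted analysis** with k covariates and N = 112.
- Residual SD = 4.3 × √(1 − R²)
- Approximate variance penalty for chance imbalance = 1 + k/(N − k − 3). For k = 3 this is 1 + 3/106 = 1.028.
- Standard error = residual SD × √1.028 × √(2/56)
- Degrees of freedom = 110 − 3 = 107, with t = 1.982
- Power from the noncentral t with noncentrality 2.3 / standard error

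Example at R² = 0.10: residual SD = 4.079; with the penalty, 4.079 × 1.014 = 4.137; standard error = 0.782; half-width = 1.982 × 0.782 = 1.55; noncentrality = 2.94; power = 83.0%.

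**3. Results at 56 per arm, three covariates.** The last column is 3 minus the half-width, the observed difference below which noninferiority is shown.

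| Analysis | Power | Half-width (mmHg) | Passing difference (mmHg) |
|---|---|---|---|
| Unadjusted t-test | 80.1% | 1.61 | 1.39 |
| Adjusted, R² = 0 | 79.0% | 1.63 | 1.37 |
| Adjusted, R² = 0.05 | 81.0% | 1.59 | 1.41 |
| Adjusted, R² = 0.10 | 83.0% | 1.55 | 1.45 |
| Adjusted, R² = 0.20 | 87.1% | 1.46 | 1.54 |

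Break-even with the t-test is at R² of about 0.03. At R² = 0.10 the precision equals that of 56 / (0.90 × 1.028) = 60.5 unadjusted patients per arm, about 4.5 more than planned.

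**4. Sensitivity to a fourth term.** Institution also belongs in the model. Randomisation is stratified on it, so little of the imbalance penalty should apply to it. Charging the full penalty anyway (k = 4; 1 + 4/105 = 1.038) gives 78.6%, 80.6%, 82.7% and 86.8% at the same four R² values, with half-widths 1.64, 1.60, 1.56 and 1.47 mmHg and break-even at about 0.04. The conclusion does not change.

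**The case against.** The strongest reply is that nothing here is wrong. A t-test is valid under 1:1 randomisation, the sample size was built for it, and it delivers the stated power. That stands. A reader might infer that the trial is underpowered or that its interval is certainly too wide. The documents support neither: the 56 per arm reproduces, and any gain depends on an R² they do not give. Below about 0.03 the adjusted model has slightly less power than the planned test.

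Three further objections also stand and limit the proposal.

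- **Preoperative mean gradient.** It is collected and looks like a natural baseline value. However, it is measured across the native valve, which is excised at surgery, so it is not a baseline of the prosthetic gradient. Eligibility does not require stenosis, so it may mainly reflect the type of native valve disease. It is the weakest candidate and is left out.
- **Institution.** A model with patient covariates but without the only stratification factor would be incomplete, so institution is included.
- **Missing 1-year echocardiograms.** It is tempting to say that adjustment repairs imbalance caused by the 20% loss. It does so only where the covariates themselves account for that loss. In general, a model fitted to patients with an observed outcome does not remove bias from missing outcomes.

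The objection does not remove the case for prespecifying. The covariates are already collected, the worst case is small, and deciding now prevents a choice after the data are known.

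**Conclusion.** The point holds as a recommended improvement to a valid analysis. Adjusting for LVEF, BSA and sex costs about 1 power point if they explain nothing (80.1% to 79.0%). It gains about 1, 3 and 7 points at R² of 0.05, 0.10 and 0.20, with the half-width falling from 1.61 to 1.59, 1.55 and 1.46 mmHg.

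These figures rest on the plan's SD of 4.3, true difference of 0.7 and 56 evaluable per arm, on an approximate imbalance penalty, and on an R² that is purely assumed. The facts that the test is unadjusted, that the covariates are collected and that no adjusted analysis is planned come directly from the documents. Whether precision is actually being lost cannot be settled from them.

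**What to change.** Before outcome data are seen, amend the SAP's statistical analysis paragraph and Protocol section 10, 7) Efficacy along these lines:

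- The primary analysis is a linear model of 1-year AVMPG on randomised valve, with institution and preoperative LVEF, BSA and sex as fixed, prespecified covariates. The native-valve gradient is not included.
- Noninferiority is concluded if the upper one-sided 97.5% confidence limit of the adjusted mean difference is below 3 mmHg in both the ITT and the PP set.
- A missing covariate value is filled by simple imputation from the baseline data, without using treatment arm or outcome, so that no patient leaves the model for that reason.
- The unadjusted t-test is reported as a supportive analysis.
- The sample size stays at 70 per arm, because R² is unknown and no saving should be assumed.

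In a linear model the adjusted coefficient targets the same mean difference, so the margin needs no change. The text should not claim that adjustment corrects bias from missing 1-year echocardiograms.

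The cost is wording in two documents and the possible loss of about 1 power point. No new data item, visit or patient is needed.

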 - Early clinical outcomes: op mortality, op morbidities (low cardiac output, bleeding reoperation, perioperative myocardial infarction, perioperative stroke, acute kidney injury, respiratory complications, postoperative atrial fibrillation, and mediastinitis)

- Echocardiographic measurements: Effective orifice area, mean pressure gradient, peak pressure gradient, LA dimension, LV ejection fraction, LV end diastolic dimension, LV end systolic dimension, pulmonary artery systolic pressure, TR severity, etc.
- Electrocardiography: 1st, 2nd and 3rd AV block, bundle branch block

5) 1-year follow-up data

- Clinical outcomes: all-cause mortality, cardiac death and major adverse events (valve-related mortality, structural valve deterioration, nonstructural dysfunction, thromboembolic and bleeding events, prosthetic valve endocarditis, AV reintervention or the need for a new permanent pacemaker or defibrillator within 14 days after the index operation), last follow-up date, New York Heart Association functional class
- Echocardiographic measurements: Effective orifice area, mean pressure gradient, peak pressure gradient, LA dimension, LV ejection fraction, LV end diastolic dimension, LV end systolic dimension, pulmonary artery systolic pressure, TR severity, etc.
- Electrocardiography: 1st, 2nd and 3rd AV block, bundle branch block

※ Primary clinical endpoint

mean pressure gradient across the aortic valve (AVMPG) on 1-year echocardiographic follow-up

※ Secondary clinical endpoint

the effective orifice area (EOA) on 1-year echocardiographic follow-up

operative mortality, operative morbidities

1-year clinical outcomes (all-cause mortality, cardiac death and major adverse events)

3) Differences from previous treatments and studies

When compared with previous treatments, the operative strategies and perioperative management are identical, but only the bioprostheses used in the treatments are different.

When compared with previous studies, all studies previously performed were prospective single-arm designs or retrospective studies. To the best of our knowledge, the present study is the first prospective randomized controlled trial comparing results of AVR using the Avaluus™ valve with those using another bovine pericardial valve that has been used worldwide.

4) Risks associated with the study

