μ_2 = mean AVMPG of the control group on 1 – year echocardiographic follow – up

σ_1 = standard deviation of AVMPG of the study group on 1 – year echocardiographic follow – up

σ_2 = standard deviation of AVMPG of the control group on 1 – year echocardiographic follow – up

δ : noninferiority margin

※ Primary clinical endpoint

mean pressure gradient across the aortic valve (AVMPG) on 1-year echocardiographic follow-up

※ Secondary clinical endpoint

the effective orifice area (EOA) on 1-year echocardiographic follow-up

operative mortality, operative morbidities

1-year clinical outcomes (all-cause mortality, cardiac death and major adverse events)

The primary endpoint of the PROVE-PERI trial is AVMPG on 1-year echocardiographic follow-up. The secondary endpoints are the EOA on 1-year echocardiographic follow-up and 1-year clinical outcomes including all-cause mortality, cardiac death and MAEs.

The study is designed to have 80% power to detect 1-year AVMPG of 12.6 ± 4.3 mmHg for the study prosthesis [2] and 11.9 ± 4.3 mmHg for the control prosthesis, [4-6] with a 1-sided type I error of 2.5% and a noninferiority margin of 3mmHg. The noninferiority margin is determined by the values of 15mmHg for AVMPG of clinically significant aortic stenosis [7] and 12mmHg for AVMPG of the control prosthesis. Fifty-six patients in each group are needed to complete the study cohort. Allowing for a 20% dropout rate during the 1-year follow-up, we determine that the recruitment of 70 patients in

each group was necessary.

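### Secondary and operative comparisons are judged at P < .050 with no testing order, link to the primary or exploratory label, and the SAP's two secondary lists disagree (4 outcomes or 13)

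*SAP*

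**What the plan says.** **Threshold.** The SAP's statistical paragraph (just before its references) assigns chi-square and Fisher tests to categorical variables and t or Mann-Whitney tests to continuous ones. It then describes the noninferiority test and the 1-year clinical comparisons, and adds: "A P value of $< .050$ will be considered statistically significant". Protocol section 10, item 7 (Efficacy) closes the same way: "A P value of $< .050$ was considered statistically significant". Neither document has a multiplicity adjustment, a hierarchy, a gate on the primary, or a statement that secondary results are exploratory.

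**Secondary lists.** The SAP's bulleted list, after the sample size section, has EOA, the 1-year clinical outcomes and "operative mortality, operative morbidities". The paragraph directly below it omits the operative outcomes: "The secondary endpoints are the EOA on 1-year echocardiographic follow-up and 1-year clinical outcomes including all-cause mortality, cardiac death and MAEs". The protocol is split in the same way. Section 10, item 2 matches the longer list. The protocol summary matches the shorter one and puts the operative outcomes under Safety, as do section 10, item 6 and section 11, item 2.

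**Primary.** "The primary endpoint of the PROVE-PERI trial is AVMPG on 1-year echocardiographic follow-up". It is tested "under the one-sided significance level of 0.025", and protocol section 10, item 7 adds: "The primary endpoint will be concluded as 'noninferior' if both ITT and PP analyses confirm the noninferiority".

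**The concern.** The plan fixes neither how many secondary comparisons there are nor what a small P value on one of them entitles the authors to say. EOA is in the trial's title and is the first-named secondary, so a claim of superiority on it is foreseeable. As written, such a P value may be called statistically significant whether or not noninferiority is shown. So may an isolated P < .050 on one of nine operative outcomes. At stake is the credibility of any secondary claim that one valve is better or safer.

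**Working it through.** **1. Group size.** The plan's formula gives n = (1.96 + 0.8416)² × (4.3² + 4.3²) / ((12.6 − 11.9) − 3)² = 7.849 × 36.98 / 5.29 = 54.87, so 55. The t-based calculation gives 56 (power 80.1% at 56, 79.4% at 55), and 56 / 0.80 = 70. The stated sample size therefore reproduces. I use 70 per arm below, taking every patient as evaluable.

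**2. Number of tests.**
- SAP prose: EOA, all-cause death, cardiac death, major adverse events (MAEs) = 4.
- SAP bulleted list and protocol section 10, item 2: those 4 + operative mortality + 8 named morbidities = 13.

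**3. Nominal ceiling.** With independent tests, each of size exactly 0.05:
- 4 tests: 1 − 0.95⁴ = 18.5%
- 13 tests: 1 − 0.95¹³ = 48.7%

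**4. Allowing for sparse tables.** All outcomes except EOA are binary and several are rare, so the true size of their tests is below 0.05. I enumerated all 71 × 71 tables at 70 per arm under equal event rates. The rule was chi-square without correction when expected counts are at least 5, and Fisher otherwise. The documents say only that tests are chosen as appropriate, so this switch is an assumption. The event rates are also assumptions.

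| Outcome | Low rate (size) | High rate (size) |
|---|---|---|
| Operative death | 1% (0.0001) | 3% (0.0057) |
| Low cardiac output | 3% (0.0057) | 10% (0.0493) |
| Bleeding reoperation | 3% (0.0057) | 8% (0.0456) |
| Myocardial infarction | 1% (0.0001) | 3% (0.0057) |
| Stroke | 1% (0.0001) | 3% (0.0057) |
| Acute kidney injury | 5% (0.0221) | 20% (0.0509) |
| Respiratory | 5% (0.0221) | 15% (0.0494) |
| Atrial fibrillation | 30% (0.0516) | 50% (0.0515) |
| Mediastinitis | 1% (0.0001) | 2% (0.0015) |
| All-cause death, 1 year | 2% (0.0015) | 6% (0.0319) |
| Cardiac death, 1 year | 1% (0.0001) | 3% (0.0057) |
| MAE, 1 year | 8% (0.0456) | 20% (0.0509) |

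**5. Chance of at least one false significant result** = 1 − 0.95 (for EOA) × product of (1 − size):
- 4 outcomes, low: 1 − 0.95 × 0.9985 × 0.9999 × 0.9544 = 9.5%
- 4 outcomes, high: 1 − 0.95 × 0.9681 × 0.9943 × 0.9491 = 13.2%
- 13 outcomes, low: 1 − 0.95 × 0.9999⁵ × 0.9943² × 0.9779² × 0.9484 × 0.9985 × 0.9544 = 18.9%
- 13 outcomes, high: 1 − 0.95 × 0.9943⁴ × 0.9507 × 0.9544 × 0.9491² × 0.9506 × 0.9485 × 0.9985 × 0.9681 = 33.8% (unrounded sizes)

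Midpoints of the listed rates give 28.5% for 13 outcomes.

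**6. Sensitivity.**
- Fisher throughout, same rates: 13.6% to 23.3% for 13 outcomes.
- A different set of assumed rates (1-year death 2–10%, cardiac death 1–5%, MAE 10–20%, operative events other than atrial fibrillation 1–20%, atrial fibrillation 30–50%): 9.8–16.2% for 4 outcomes and 17.9–40.7% for 13.
- Correlation: I simulated one shared patient factor (latent correlation 0.3 or 0.5), with operative and cardiac deaths nested in all-cause death and EOA independent. The 13-outcome figures were 18–19% at low rates and 31–33% at high rates, slightly below the independent case.

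**The case against.** The strongest reply is that the consequence is limited. There is one primary endpoint with its own one-sided 0.025, and both ITT and PP must confirm it. A reader might infer that the secondary tests inflate the trial's type I error. They do not, because no secondary result enters the noninferiority rule. A reader might also infer that the sponsor intends to claim a secondary difference after a failed primary. Neither document says so. The plan only leaves room for it.

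Thirteen is also the largest reading. In both documents the threshold sentence directly follows the one on 1-year clinical outcomes. Read narrowly, it covers only those three tests: 1 − 0.9985 × 0.9999 × 0.9544 = 4.7% at low rates and 1 − 0.9681 × 0.9943 × 0.9491 = 8.6% at high rates. The broad reading is plausible, since the SAP paragraph covers all group comparisons, but it is not the only one.

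Nine of the 13 are also safety outcomes, and familywise control over safety comparisons is not a settled requirement, because adjustment can hide harm. That stands. It argues for classifying these outcomes clearly and against a formal correction across them.

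Finally, cardiac death is part of all-cause death, MAEs include valve-related mortality, and operative deaths recur at 1 year, so independence is not strictly true. In the simulation above the effect was small. Other dependence structures could change the figures more.

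What remains is the text itself: a stated significance rule with no order or label, applied to a set of outcomes that the SAP defines in two ways.

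**Conclusion.** The point holds as a weakness in how secondary results may be reported and interpreted, and should be corrected. The noninferiority conclusion is untouched.

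The size depends on which list applies: about 10–13% for the 4-outcome list and about 19–34% for the 13-outcome list, with 14–23% for the latter if Fisher's test is used throughout. The nominal ceilings are 19% and 49%. It would be tempting to quote 19–34% as the plan's false-positive risk without conditions. The documents do not support that. The range needs the longer list with each morbidity tested singly, event rates that the documents do not supply, independence, a chi-square/Fisher switch that is not written down, and 70 evaluable patients per arm. The conflict between the two lists needs no assumption and has to be resolved in any case.

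**What to change.** 1. Keep one secondary list, identical in the protocol summary, protocol section 10 and the SAP. Classify operative mortality and the operative morbidities consistently as either secondary or safety.
2. Replace the P < .050 sentence in both documents with wording such as: *EOA at 1 year will be tested at two-sided .05 only if noninferiority on the primary endpoint is concluded. All other secondary and safety outcomes will be reported as estimates with 95% confidence intervals. Their P values are unadjusted and descriptive and will not be called statistically significant.*

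The noninferiority test already has its own stated level, so it needs no further sentence. If no formal claim on EOA is wanted, putting EOA under the descriptive rule as well would be enough.

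The cost is wording in the SAP and protocol, with no change to sample size, data collection or safety monitoring. The downside is that an isolated P < .05 on a complication can no longer be headlined as significant. The estimates and intervals would still show any safety signal.
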